Specific Aim 1 (Primary Aim): To determine the effectiveness of ZNS treatment in reducing drinking on the primary outcome measure: drinks per week (measured using the Timeline Followback Method), for eight weeks at a target dose of 600 mg of ZNS daily for 160 heavy-drinking, alcohol-dependent veterans. We hypothesize that ZNS treatment will reduce the heavy drinking days per week and the total drinks per week significantly more than the placebo and that the benefits will persist at three months follow-up after treatment.

Specific Aim # 2 (Secondary Aim): To examine the effects of ZNS treatment on heavy drinking days per week, , percentage of subjects with no heavy drinking days (PSNHDD) the urge to drink (craving), biomarkers of alcohol intake, clinical global impression, medication tolerability, and other patient-centered outcomes. We hypothesize that ZNS will demonstrate significantly greater improvements than the placebo on these measures by the treatment endpoint as well as at follow-up.

Specific Aim #3 (Secondary): To use telephone-based daily process data collection to elucidate the mechanism of action of ZNS as it relates to changes in craving, anxiety, and genetic variation. *This method has been shown to elucidate the mechanism of action of topiramate, as well as its pharmacogenetic interactions.* We hypothesize that ZNS' effects will be moderated by genetic variation, craving, and anxiety, but mediated through changes in self-efficacy to reduce heavy drinking.

Specific Aim #4 (Exploratory): The exploratory aim is to examine the pharmacogenetic interactions between ZNS and the therapeutic response. We hypothesize that both the long (L) allele of the VNTR polymorphism in exon 3 of the *DRD4* gene and the CC genotype of the *DBH* rs1611115 (C-1021T) SNP will show a pharmacogenetic effect with ZNS, as evidenced by a greater reduction in drinking than for the short (S) allele and T carriers respectively.

Specific Aim #5 (Exploratory) To compare ZNS and placebo-treated subjects on pre- and post-treatment changes in measures of stress-reactivity (i.e., stress-induced anxiety, alcohol craving, autonomic nervous system activity), cue-elicited craving, and impulsivity. We hypothesize that ZNS will attenuate stress-reactivity, cue-elicited craving, and impulsivity more than placebo in a stress laboratory paradigm, and that attenuation of those measures will be associated with reduction in drinking.

4. BACKGROUND:

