6.D.2. Visit 1 (Baseline Visit): N= 160 subjects will be randomly assigned to receive either ZNS (80 subjects) or placebo (80 subjects). We will use blocked stratified randomization with treatment site (VA Connecticut versus Bedford) and the use of other psychotropic medications (e.g., antidepressants) as the stratification variables, with block sizes of 4 in each stratum to achieve treatment balance throughout the randomization process. Within 21 days after the screening visit, eligible subjects undergo a two-hour pre-treatment assessment (described below). At the baseline visit, subjects will complete a packet of questionnaires. Subjects will receive their first medication management session and first supply of study medication during a treatment session (visit 1) scheduled on the same day, following completion of the baseline assessments.

Subjects will begin study medication (i.e., ZNS or matching placebo) at an initial dosage of 100mg/day. All subjects will be asked to bring any remaining capsules and the study medication container to their next and all subsequent clinic visits, so that capsule counts can be used to measure compliance. The subject begins 6-week titration phase, during which the dosage will be titrated up as indicated above and in Table 1. Subjects will be paid a nominal but fair amount of money in compensation for all visits, including follow-up visits. Table 1 shows the titration schedule:

TABLE 1: Medication Titration Schedule

Week	Placebo	Zonisamide dose
1	One capsule daily	100mg QHS
2	Two capsules daily	200mg QHS
3	Two capsules daily	200mg QHS
4	Three capsules daily	300mg QHS
5	Three capsules daily	300mg QHS
6	Four capsules daily	400mg QHS
7	Four capsules daily	400mg QHS
8-9	Five capsules daily	500mg QHS (Target dose)
10-16	Five or Six capsules daily, 7 weeks duration	Continue 500mg daily or optional increase to 600mg QHS, 7 weeks duration
17-18	TAPER: Decrease capsules by one a day every 3 days, over a period of up to 15 days	TAPER: Decrease dose 100mg every 3 days, over a period of up to 15 days

Table 1 notes: 7 weeks of titration to the 500mg daily target dose. 9 weeks at the target dose with the option to increase to 600mg daily after two weeks at target if treatment response is suboptimal and there are no significant side effects (no current moderate to severe AE's with 500mg daily).

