We will use the percentage of subjects with no heavy drinking days (**PSNHDD**) as the primary outcome variable. This outcome is the FDA recommended endpoint for pivotal trials, and is described in Falk et al., (2010). The PSNHDD can be derived from each subject's TLFB data. An important initial consideration in considering effectiveness will be to identify baseline differences between groups that may have occurred despite randomization. **Successful outcomes during the treatment trial will be defined in terms of a statistically significant difference on the primary outcome measure: PSNHDD, compared during the 8 weeks of active treatment at the target dose, allowing for a 6 week grace period for the medication titration.** For all analyses, heavy drinking days will be defined as follows; for men > 5 drinks in a day and for women > 4 drinks in a day. Patients will be followed irrespective of whether they continue to receive medication treatment, so that analysis will include all data available for the 8-week treatment period. The analysis will be **intent-to-treat**, and dropouts will be considered as having relapsed to heavy drinking. We will use a logistic regression analysis with PSNHDD as a categorical dependent variable. Medication condition (placebo or ZNS) will be the main independent variable, and we will include the variables of early onset of alcoholism (EOA, binary), and the use of additional psychotropics (e.g., antidepressants, a binary variable) as covariates. The α will be set at .05 for the primary outcome variable. Between site differences will be explored.

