All secondary outcome analyses will be by intention to treat, a conservative approach that is aimed at avoiding an overestimation of the treatment effect and will include all subjects that take any medication and provide drinking data for at least one week. The use of multilevel repeated measure statistical models may increase the study power and potential to detect a treatment effect. This type of repeated-measures analysis 1) provides missing-data imputation procedures that are both conservative and logical; 2) allows for the measurement of the exact time that a given patient is measured at baseline and follow-up points, which need not be the same among patients; 3) plots and analyzes linear and non-linear time-course functions both overall and for subgroups of patients based on each patient's best estimate linear and non-linear regression line plots. We will use all available data on individuals and thus dropouts provide data until the point of dropout. The best-fitting variance-covariance structure between the repeated measures will be selected based on Schwartz-Bayesian Information Criterion (BIC). We will compare dropout patterns between groups and if there are concerns of informative dropout and/or informative intermittent missing data, we will use pattern mixture models (Hedeker and Gibbons, 1997) to perform sensitivity analyses to our main analyses. Adherence to the medication will be evaluated and factored into the analysis. We will evaluate and compare both medication conditions (placebo, ZNS) for percentage of prescribed pills taken. We do not expect a difference, but if one is found, we can then perform additional analysis on the main outcome variables to estimate treatment effects adjusted for percent pills taken. The number of MM sessions attended will be recorded and analyzed similar to the medication adherence.

The three-month follow up data will be gathered using a retrospective TLFB at the follow-up time point, and will be analyzed using logistic regression for PSNHDD, and either linear mixed models or Hierarchical Linear Modeling (HLM) for other outcomes. We will examine that drinking data between the end of treatment and the three-month time point and use the same outcomes as the main analysis. We will be able to examine for persistent effects of ZNS on drinking behavior and related outcomes. These analyses will include pre-treatment and within-treatment drinking data as covariates to evaluate the post-treatment effects of ZNS.

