6.I.6. Sample Size And Power Estimate (Specific Aims 1-3):

For the primary outcome PSNHDD: Based on the trend in the pilot study favoring ZNS with 12 subjects in the ZNS group without relapse to heavy drinking, and only 7 in the placebo group, we estimated the power with the previously planned sample size. Based on these proportions, we should be well powered (>89%) to detect a difference in PSNHDD with 80 in each group. Since dropouts will be counted as relapsed to heavy drinking, we will still be powered at that level, regardless of the number of dropouts. Even in the event that we don't recruit as many subjects as expected (e.g., N=64 in each group, approximately) we estimate the estimated power will be about 76% to detect a difference between the medication and placebo.

For secondary outcomes: Based on the effect sizes from our pilot study of ZNS (showing a small effect size on heavy drinking and a moderate effect size on total drinking), we estimated that a study with **N=160** (subjects) would be well powered (>.98) to detect a significant difference on the secondary outcomes heavy drinking days per week, and total drinks per week. In our pilot study we ran a linear mixed models and found a decrease in drinking of 1.4 drinks per week for the controls versus 2.2 drinks per week for ZNS. The variance in the decrease in drinking (slope) was approximately 0.9. Assuming similar results, a Monte Carlo simulation in Mplus showed that with a sample of 160 subjects evenly split between groups and measured weekly over 12 weeks there is power of 0.98 to detect a significant difference in slopes between groups. Also, in our pilot study we found a decrease in heavy drinking days per week of 0.2 for the controls versus 0.3 for ZNS. The variance in the decrease in drinking (slope) was about 0.1. Assuming similar results, a Monte Carlo simulation in Mplus showed that with a sample of 160 subjects evenly split between groups and measured weekly over 12 weeks there is power of 0.99 to detect a significant difference in slopes between groups. **Even if dropouts reached 40%, we will be well powered (>.80) for detecting differences on secondary outcomes.**

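### The secondary analyses are called intention to treat, but two post-randomisation conditions make the set modified intention to treat and bar randomised patients who have usable drinking data

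*Combined protocol and SAP*

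**What the plan says.** On the secondary outcomes, Section 6.I.2 states: "All secondary outcome analyses will be by intention to treat, a conservative approach that is aimed at avoiding an overestimation of the treatment effect". The sentence continues that these analyses "will include all subjects that take any medication and provide drinking data for at least one week".

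For the primary PSNHDD analysis, the same section sets no dosing or data condition. It says "Patients will be followed irrespective of whether they continue to receive medication treatment" and "dropouts will be considered as having relapsed to heavy drinking". Section 6.I.6 then claims that power with 80 per group holds however many patients drop out.

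Under Section 6.D.2, randomisation belongs to the baseline visit, and patients receive their "first supply of study medication during a treatment session (visit 1) scheduled on the same day". They take the capsules home, so a randomised patient can take none, or can fail to return with a week of drinking data.

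Three provisions bear on missing data. Section 6.I.2 compares dropout patterns between arms and allows pattern mixture models if dropout looks informative. Section 6.I.3 examines overall dropout rates. Section 6.D.4 asks every subject for an end-of-treatment evaluation in support of the intention-to-treat analyses.

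**The concern.** Intention to treat protects a comparison because membership of the analysis set is fixed at randomisation. Here membership depends on two later events, and the second is whether the outcome was supplied. The claim that the approach is conservative therefore does not follow: if early leavers drink more and the arms lose different numbers, removing them can flatter either arm.

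The plan would also report two populations under one label. A patient who leaves in week 1 is a failure for PSNHDD and absent from drinks per week and heavy drinking days per week. Those outcomes carry weight, because Section 6.I.2 would count significant and clinically meaningful results on them as a partial success for the drug.

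The protocol's own background shows that dropout handling can matter. Section 4.B.1 reports that, when topiramate dropouts were assumed to return to baseline drinking, the difference in heavy drinking days fell from 16.19% to 8.44%. The loss is 16.19 − 8.44 = 7.75 points, and 7.75/16.19 = 48%. That figure covers all dropouts, not only those lost in the first week, so it shows sensitivity and not an expected size here.

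**Working it through.** **1. What the primary analysis relies on.** Inputs from Section 6.I.6 are the pilot counts, "12 subjects in the ZNS group without relapse to heavy drinking, and only 7 in the placebo group", and 80 per group. Section 3 gives a pilot of N = 40; 20 per arm and a two-sided α of 0.05 are assumptions. The rates are then 7/20 = 0.35 and 12/20 = 0.60, with mean 0.475.

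Power = Φ{[0.25 − 1.96·√(2·0.475·0.525/80)] / √[(0.35·0.65 + 0.60·0.40)/80]} = Φ{(0.25 − 0.1548)/0.0764} = Φ(1.246) = 89.4%.

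This reproduces the stated power of more than 89%.

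**2. Whether that claim could survive the secondary filters.** With the same rates and formula, but 5% or 10% of patients removed:

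- 76 per arm: 87.8%
- 72 per arm: 86.0%

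Both fall below the stated figure. The claim that dropout leaves power untouched therefore makes sense only if all 80 per arm stay in the denominator. No section defines the primary set as all randomised in so many words; this is an inference from how Section 6.I.2 treats dropouts and from Section 6.I.6.

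**3. Who is treated differently.** The filter does not say when the week of data must fall. Section 6.C requires a 90-day pre-treatment Timeline Followback (TLFB), so if pre-treatment data counted, the data condition would exclude nobody. It is read here as a week on treatment.

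- Never doses, but reports drinking: in the PSNHDD analysis; barred from the secondary analyses although data exist.
- Doses, gives part of a week: in the PSNHDD analysis, as a failure if a dropout; barred from the secondary analyses, and the partial data are discarded.
- Gives no on-treatment data: a failure for PSNHDD; absent from the secondary analyses with or without the filter.

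For the first two groups the exclusion is a choice. TLFB is retrospective and collected weekly (Section 6.F.2(b)), drinking is also reported daily by telephone (Section 6.F.2(e)), and the end-of-treatment evaluation is sought from everyone.

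**4. How many.** The documents give no rate of never-dosed or under-one-week patients. Over an assumed 2.5%, 5%, 10% or 15% of 160, the secondary set would hold 156, 152, 144 or 136 patients. The effect on an arm difference also needs the split by arm and the drinking of those excluded. Neither is given, so no bias figure can be derived.

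**5. Whether adding baseline as a repeated measure would be enough.** With a common baseline mean, the likelihood factors into the distribution of baseline and the distribution of later drinking given baseline and arm. A patient with baseline only enters the first factor. The arm effect sits in the second, and the plan's model already controls for pre-treatment drinking. With an unstructured covariance such patients add nothing to the arm contrast; with a simpler structure they add very little. Everyone is nominally included, but informative early loss is not corrected.

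**The case against.** The strongest reply is that the practical effect is slight. Section 6.I.2 focuses the mixed models on the eight weeks at target dose, after a titration grace period. A patient who leaves in week 1 and gives nothing later has no outcome in that window whether or not the filter exists, and the same is true of someone who leaves in week 3 and passes it. This stands. It confines the filter's direct effect to patients who have data but are barred; partial-week data matter mainly where a model uses the titration weeks.

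Next, the dosing condition is low risk. Treatment is blinded and supplied on the day of the baseline visit, so never starting can hardly depend on arm. This also stands; the data condition is the more serious of the two.

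It is also fair that scoring dropouts as failures suits a binary endpoint and has no direct counterpart for drinks per week. Different handling of missing values is not an error in itself. A different patient set under the same name is.

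Finally, there are safeguards. The pattern mixture models are conditional, however, and nothing says that they restore excluded patients. Comparing dropout rates describes the loss without repairing it. No all-randomised analysis of the secondary outcomes is planned.

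A reader might infer that the rule tilts the secondary results towards zonisamide by some definite amount. The documents do not support that. It would need unequal early loss and heavier drinking among those lost, and they report neither. Week 1 is the lowest titration step, and Section 4.B.2 says that few participants dropped out of earlier zonisamide studies. Similar losses in both arms would largely cancel.

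**Conclusion.** The point holds as a matter of definition and analysis set. The secondary set is modified intention to treat, the description of it as conservative is not earned, and randomised patients with usable drinking data are left out for no stated reason. The size of any resulting bias cannot be computed from the documents and may be small. The conclusion rests on two readings: that the required week of data is on treatment, and that the primary analysis keeps all randomised patients.

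A reader might also infer that the primary result is affected, since Specific Aim 1 reads "To determine the effectiveness of ZNS treatment in reducing drinking on the primary outcome measure: drinks per week". The sentence in Section 6.I.2 governs secondary outcomes only, and that section makes PSNHDD primary and drinks per week secondary. The conflict over which outcome is primary is a separate issue and needs its own reconciliation; it does not make this point larger.

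The change is worth making because it is cheap and can alter results for the patients now barred.

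**What to change.** In Section 6.I.2:

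- Delete both conditions. Define one set for primary and secondary outcomes: all randomised patients, by assigned arm, with every available TLFB observation used whatever the dosing.
- For patients with no on-treatment drinking data, report numbers and reasons by arm.
- Pre-specify a sensitivity analysis that imputes their drinking, for example as a return to baseline. Section 4.B.1 already cites such an analysis as the more conservative one, and baseline TLFB is already collected. Entering baseline as a repeated measure should not stand in for this.
- Keep the present set as a sensitivity analysis, labelled modified intention to treat.

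The cost is revised wording and a little more analysis, with no new data collection. Including patients who never dosed will dilute the effect estimate slightly, which is the ordinary price of an intention-to-treat comparison.

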The potential utility of anticonvulsants to reduce the risk or severity of relapse was demonstrated initially in a 12-month pilot study of carbamazepine by Mueller, Stout (21), who found the drug to be superior to a placebo with respect to a number of drinking outcomes. A 12-week, double blind, placebo-controlled pilot study of divalproex in alcohol-dependent individuals by Brady, Myrick (22) showed that divalproex reduced irritability and had a slight effect on reducing the risk of relapse into heavy drinking when compared with a placebo treatment. Johnson, Ait-Daoud (23) demonstrated the efficacy of topiramate for AD in a double blind, randomized, placebo-controlled trial. In a follow-up, larger (N=371), multi-center, randomized placebo-controlled trial (24), topiramate was again found superior to a placebo with a moderate effect size. This fourteen-week trial of topiramate, with dosage up to 300mg/day, showed an effect size of 0.52 in the reduction of the percentage of heavy drinking days for treatment-seeking alcoholics who received 14 weeks of concomitant brief behavioral compliance therapy (a minimal behavioral intervention aimed at enhancing medication compliance) (4).

A more conservative analysis of the topiramate data, which assumed a return to baseline drinking levels for dropouts, reduced the effect on percentage of heavy drinking days by almost half (a difference in mean reduction of 16.19% of heavy drinking days compared to 8.44% reduction in the conservative analysis), and some critics have brought attention to the frequency and severity of side effects of this medication, which limits its use and effectiveness (24-26). Thus, although topiramate is effective, its use is significantly limited by its side effects. Research demonstrating effectiveness of topiramate in veterans is lacking. A recent study in civilians showed a moderate dose of topiramate to be fairly well tolerated and efficacious (27).

Recently, a placebo controlled trial of the anticonvulsant gabapentin for civilians with AD showed significant benefit with the medication, although the dropout rate was high (28). Gabapentin often requires a three-times-daily dosage regimen, which decreases the likelihood of adherence in patients. In contrast, ZNS has a long half-life and is easily administered once daily.

4.B.2. The Rationale For ZNS Treatment Of AD In Veterans:

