6.D.4. Visits 2-17 (Treatment and End-of-Treatment Visits): Subjects will return weekly for study visits to meet with the research nurse, complete questionnaires, and receive medical management (MM, described below). At study midpoint (i.e., 8 weeks after starting medication), another CBC, and chemistry/electrolyte panel (including a serum GGT), will be obtained. Urine drug screens will be checked weekly, and pregnancy tests (in all females of reproductive potential) are repeated monthly. At the end of week 16 (endpoint), subjects will complete the packet of questionnaires and will be interviewed by the research evaluator concerning their alcohol-related symptomatology using the Alcohol Use Disorders section of the SCID over the past 30 days. Subjects will also be interviewed by the research nurse about their use of concomitant medications, occurrence of adverse events, compliance with the protocol, and their assessment of the effectiveness and acceptability of the treatment procedures. A blood sample for measurement of serum GGT and metabolic labs will be obtained to provide an index of potential hepatic effects and to assess the validity of self-reported drinking. A urine drug screen and urine pregnancy screen (in all females of reproductive potential) will be obtained at this time as well. The nurse and study physician will monitor continuing adverse events to their resolution. Subjects requesting (or clearly needing) additional treatment for alcohol problems are (if clinically indicated) discontinued from the study protocol and referred to local treatment centers. Similarly, at the end of the treatment trial, subjects whose drinking requires continued treatment will be referred for such treatment. All subjects will be asked to complete an end-of-treatment evaluation to facilitate planned intention-to-treat analyses. All subjects will be informed of these procedures prior to study enrollment.

6.D.5. Visit 10b (Stress Lab Session 2): This visit will occur between weeks 8-16 of being on the study medication. The session will use the same audio tapes created for the baseline stress lab and the session will be identical to the baseline stress lab (assessments), with the exception of the randomized order of the presentation of the audio tapes.

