Protection Against Risk To Subjects: Inclusion/exclusion criteria, and the use of experienced, well trained research assistants, psychologists, and research nurses in the initial screening helps to avoid the acceptance of subjects with insignificant alcohol use into the study. Careful medical and psychiatric evaluation minimizes the likelihood of including individuals with illness that contraindicates participation in the research. Repeated measurement of laboratory parameters will enable the early identification of subjects who might experience an adverse reaction that is not readily reported by the subject. Confidentiality in regard to collected materials is maintained via a numbered reference system maintained by the project director. Subjects' names appear only on a consent form and "key" form kept by the project director. Subjects are withdrawn from the study if they show severe clinical deterioration. Subjects who are removed from the study are referred to treatment at a local treatment facility (in this case most likely the corresponding VA), according to their needs and wishes. Additional safeguards are described in section 1.B above. Suicidal ideation and mood changes can occur, so subjects will be monitored closely at their weekly visits using psychometric measures of mood and suicidal ideation. The Columbia Suicide Severity Rating Scale will be used routinely to help identify subjects in need of further evaluation or intervention. Additionally, a DSMB will be employed to regularly monitor study safety (see section 5 below for more information). Subjects are allowed to continue to receive psychiatric treatment for any co-occurring disorders during the study.

8.D. BENEFITS TO SUBJECTS AND KNOWLEDGE TO BE GAINED:

Risk/Benefit Ratio:

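### The secondary mixed models' missing-data handling is labelled conservative but assumes missing at random, and its only sensitivity check depends on a between-group dropout comparison that can miss informative dropout

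*Combined protocol and SAP*

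**What the plan says.** Section 6.I.2 fits mixed models to drinks per week and heavy drinking days per week, with a random intercept and adjustment for pre-treatment drinking. It describes the secondary intention-to-treat analysis as "a conservative approach that is aimed at avoiding an overestimation of the treatment effect" and says that this type of model "provides missing-data imputation procedures that are both conservative and logical". Dropouts contribute data up to the point at which they leave. The safeguard is conditional: "We will compare dropout patterns between groups and if there are concerns of informative dropout" or informative intermittent missingness, pattern-mixture models are run as a sensitivity analysis. No criterion for concern is given, and the patterns and assumptions are not stated.

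For the primary outcome, the percentage of subjects with no heavy drinking days, the same section says "dropouts will be considered as having relapsed to heavy drinking".

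Several sections allow removal for reasons that may relate to drinking or tolerability:

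- Section 6.D.4: "Subjects requesting (or clearly needing) additional treatment for alcohol problems are (if clinically indicated) discontinued from the study protocol".
- Section 8.C (Protection Against Risk To Subjects): "Subjects are withdrawn from the study if they show severe clinical deterioration".
- Section 6.E.1: withdrawal for unacceptable side effects, severe psychological symptoms, or rule violations such as two consecutive missed visits.

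Other text points the other way. Section 6.I.2 (primary outcome) promises follow-up whether or not medication continues, and section 6.D.4 asks every subject for an end-of-treatment evaluation.

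**The concern.** A likelihood-based mixed model treats the missing weeks as predictable from the observed data, arm and baseline. In effect, a patient who leaves is assumed to have continued like similar patients who stayed in the same arm. That may be reasonable, but it is not conservative, and it differs sharply from the relapse assumption applied to the same patients in the primary analysis.

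The check that would show how much depends on this assumption runs only if comparing the arms' dropout patterns raises concern. If similar patients leave at similar times in both arms, that comparison shows nothing, whatever they drink afterwards.

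The stakes go beyond supportive results. Section 6.I.2 lets the secondary drinking measures support a conclusion of relative success for the medication. Specific Aim 1 in section 3 names drinks per week as the primary outcome measure, so the point may reach the main result.

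**Working it through.** **1. The plan's own figure.** Section 6.I.6 gives slopes of 1.4 (placebo) and 2.2 (ZNS), a difference of 0.8; slope variance 0.9; 80 per arm; 12 weekly measures; power 0.98. I assume two-sided α = 0.05, since sidedness is not stated.

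- No residual error: SE = √(2 × 0.9/80) = 0.150. Power = Φ(0.8/0.150 − 1.96) = 0.9996.
- The residual variance is not given. A residual SD of 10 adds 100/143 = 0.699 to the slope variance (143 is the sum of squared deviations of weeks 1 to 12). SE = √(2 × 1.599/80) = 0.200 and power = 0.979, which matches 0.98.
- With 40% dropout (48 per arm): SE = √(2 × 1.599/48) = 0.258 and power = 0.873, consistent with the stated >0.80.

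The 40% allowance therefore treats dropout as lost numbers only, with nothing for bias.

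**2. The plan's own example of dropout sensitivity.** Section 4.B.1 reports that setting topiramate dropouts to baseline "reduced the effect on percentage of heavy drinking days by almost half", from 16.19 to 8.44. The ratio is 8.44/16.19 = 0.52, a fall of 48%. If the 0.8 slope shrank likewise, to 0.42, power would be about Φ(0.417/0.200 − 1.96) = 0.55 with 80 per arm and 0.37 with 48.

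**3. Simple illustration, assuming return to baseline.** If a fraction d leaves each arm and those patients end with no change, the all-randomised effect is (1 − d) times the effect in those who stay. The overstatement factor is 1/(1 − d): 1.25 at 20%, 1.43 at 30%, 1.67 at 40%. With 40% ZNS and 20% placebo dropout, 2.2 × 0.6 − 1.4 × 0.8 = 0.20 instead of 0.8. This treats the printed slopes as endpoint changes and ignores data before dropout, so it is only an illustration.

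**4. Simulation of the planned model** (arm by week, baseline covariate, random intercept). Inputs from the documents: slopes 1.4 and 2.2, slope variance 0.9, 12 weeks. Assumptions: residual SD 10 (solved in step 1), entry mean 45 drinks per week, between-subject SD 15, and the dropout rates and courses below. Each case used 4 runs of 1,500 per arm, giving a Monte Carlo error of about √(2 × 1.599/6000) = 0.02.

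| Dropout and what follows | Planned model | Complete data |
|---|---|---|
| 40% each arm, back to entry level | 0.81 | 0.42 |
| 20% each arm, back to entry level | 0.82 | 0.59 |
| 40% ZNS, 20% placebo, back to entry level | 0.76 | 0.02 |
| Same drinking-based rule in both arms, rise recorded, then back to entry level (42% ZNS, 57% placebo removed) | 0.76 | 0.64 |
| Same rule, rise not recorded, then back to entry level | 0.67 | 0.73 |
| Same rule, rise recorded, earlier course then continues | 0.72 | 0.81 |
| 20% ZNS, 40% placebo, back to entry level | 0.77 | 0.89 |

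The benefit is overstated in four cases and understated in three.

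The first row can be checked by hand. A patient who declines up to a last observed week m and then returns to entry level has a fitted slope equal to the decline rate times Σ w(w − 6.5)/143, summed over weeks w = 1 to m. For m = 2 to 8 the sums are −14.5, −25, −35, −42.5, −45.5, −42 and −30. Their mean is −33.5, and −33.5/143 = −0.234. The difference is then 0.8 × (0.6 − 0.4 × 0.234) = 0.40, against 0.42 simulated. It lies below the simple 0.8 × 0.6 = 0.48 because such patients contribute a rising line, not a flat one.

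**5. The trigger.** Power to detect a difference in dropout rates with n = 80 per arm is Φ{[|p₁ − p₂| − 1.96√(2p̄(1 − p̄)/n)] / √([p₁(1 − p₁) + p₂(1 − p₂)]/n)}.

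- 40% v 30%: (0.1 − 1.96 × 0.0754)/0.0750 = −0.64, power 0.26.
- 30% v 20%: 0.31.
- 40% v 20%: 0.79.
- Equal rates: 0.05, the false-positive rate alone, although in the table's first row the effect is nearly doubled.

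**The case against.** Three stronger readings are tempting, and the documents do not support them.

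*Dropout is informative by design.* A reader might infer this from the removal rules. But section 6.D.4 applies only if clinically indicated, section 8.C does not mention drinking, and section 6.E.5 lets subjects attend twelve-step, group and day programmes while in the study. Drinking is recorded weekly by TLFB, so removal that follows recorded drinking is closer to missing at random, which a well-specified mixed model can handle. The intercept-only random effect weakens that defence, and departures after unrecorded drinking or for side effects remain open.

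*The benefit will be overstated.* The direction is not fixed. A drinking-based rule applied equally tends to remove more placebo patients, and two of the three simulated cases of that kind understated the benefit. The clearest overstatement comes from return to entry-level drinking after departures that are equal between arms or more frequent on ZNS, for example for side effects.

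*The assumption goes unchecked.* The plan has a conditional pattern-mixture analysis, promises follow-up off medication, requests an end-of-treatment evaluation, and records reasons for termination (section 6.F.2(d)). The trigger refers to patterns, not rates alone, and covers intermittent missingness, so a broad reading could catch differences in timing or reasons. That reading depends on judgement after the data are seen, and no comparison of arms helps when the patterns match.

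It is also fair that trial success is defined in section 6.I.2 by the primary outcome with dropouts as failures, that relative success also requires clinically significant effect sizes, and that secondary outcomes are Bonferroni-corrected. None of these tests the missing-data assumption. Finally, the dropout rates here are assumed, topiramate is a different drug, and section 4.B.2 reports few dropouts in earlier ZNS studies.

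**Conclusion.** The point stands in a limited form. Calling the mixed models' missing-data handling conservative is wrong: it is a missing-at-random assumption that can bias the drinking effect either way. If dropouts in both arms return to baseline, the benefit is overstated at equal dropout rates, by a factor of about 1.4 at 20% (0.82/0.59) and 1.9 at 40% (0.81/0.42) under the simulation's assumptions. The only sensitivity analysis may never run, because its trigger has no criterion, has little power for moderate rate differences, and has nothing to detect when dropout patterns are equal.

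The simulated sizes rest on assumed entry drinking, residual variance, dropout rates and post-dropout course, so they show direction and range and are not forecasts. The low power of the rate comparison needs only 80 per arm and the stated rates.

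The document also leaves unresolved whether drinking data are collected and used after withdrawal. The promise of follow-up in section 6.I.2 and the evaluation in section 6.D.4 are not reconciled with withdrawal from the study in sections 6.E.1 and 8.C, or with use of dropouts' data only up to dropout in section 6.I.2. This should be settled before analysis. It is not a flaw in the design as a whole.

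**What to change.** 1. In section 6.I.2, remove the conservative label from the mixed models' missing-data handling and state the missing-at-random assumption.
2. Delete the trigger. For both drinks per week and heavy drinking days per week, always report two sensitivity analyses beside the main result: (a) return to baseline, with weeks after dropout imputed around the subject's pre-treatment level and imputation uncertainty carried through, since a single fixed value would understate it; and (b) a pattern-mixture model with its patterns and assumptions written down in advance.
3. Require any relative-success conclusion to state whether it holds under both.
4. Reconcile sections 6.D.4, 6.E.1, 6.I.2 and 8.C on whether drinking data are collected and used after withdrawal. The withdrawal rules themselves are a clinical matter on which this point takes no position.

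Return to baseline is one defensible scenario among several. It is a natural choice because section 4.B.1 already uses it to judge topiramate. The cost is SAP wording and a little extra analysis of data already being collected. The downside is that the benefit may look smaller in the sensitivity results.
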